5.0 Study Procedures

[figure not shown]
Study design: Subjects will be asked to report to the laboratory on a three occasions, separated by a minimum of 48 hours and a maximum of 14 days. For each subject, all testing sessions will be performed at the same time of day. Prior to each testing session, subjects will be asked to abstain from caffeine consumption for 12 hours. Subjects will also be asked to avoid alcohol consumption for 24 hours before testing, be at least 3-hour post prandial and avoid high-intensity exercise during the 24 hours leading to the exercise testing. Finally, subjects will be asked to consume a similar diet the night before, and the morning of, Sessions 2 and 3.

The first session of testing includes: informed consent completion, completion of a general questionnaire, completion of a standard medical questionnaire, measures of height and weight, measures of body composition, resting pulmonary function testing, completion of a maximal oxygen uptake test on a cycle ergometer (in normoxia) with measures of respiratory flow-volume characteristics, and familiarization with the 5km cycle ergometry time trial (TT) in hypoxia (14.3% O₂, simulating 3000m). This session is expected to take approximately 60-90 minutes.

The 2nd and 3rd sessions will include Cetirizine (10 mg) or placebo ingestion, 60 minutes of rest (time required to reach peak Cetirizine plasma levels), a blood draw to measure plasma histamine levels, a brief warm-up, two 5-minute constant-load cycle ergometry exercise bouts at moderate intensity in hypoxia with 5-minute of passive recovery following each exercise bout, a 5km cycle ergometry TT in hypoxia, and a post-exercise blood draw to measure plasma histamine levels. These sessions are expected to take approximately 120 minutes each.

During the hour between Cetirizine / placebo ingestion and the beginning of the testing trial, subjects will be allowed to rest comfortably in the lab. Sessions 2 and 3 will be randomized and counterbalanced.

A graphical timeline is below:

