on the cycle ergometer at a self-selected speed for 10 minutes. Following the warm-up, subjects will be fitted with a chest strap heart rate monitor, an oro-nasal face mask, a pulse oximeter sensor, and near-infrared spectroscopy optodes. Subjects will then be asked to complete two 5-minute cycling bouts at a constant, moderate intensity (as will be determined individually according to each subject's maximal oxygen uptake test performed on Session 1, details below). Subjects will be allowed 5 minutes of passive recovery after each of the 5-minute cycling bouts. Following the second recovery period, subjects will be asked to ride 5km, completing the distance in as short of a time as possible. Subjects will be allowed to shift gears on the bike at will and pedal at any RPM desired. Feedback on distance completed will be shown on a video monitor and verbally announced every 1km. During the TT, respiratory flow-volume measures will be completed by having the subjects complete two inspiratory capacity (IC) maneuvers near the end of each kilometer of the TT. Immediately following the TT, approximately 5 ml of blood will be drawn from an antecubital vein.

Demographic and screening variables: Age, height, weight, sex, body mass index, body composition (estimated percent lean body mass and fat mass), pulmonary function measures (total lung capacity, vital capacity, forced expiratory volume in one second, lung diffusing capacity, and maximal voluntary ventilation).

Dependent variables: exercise metabolic measures (VO₂, VCO₂, ventilation, heart rate), dyspnea and rating of perceived exertion during the 5km TT, time to completion of the 5km TT, power output during the 5km TT, muscle oxygenation, plasma histamine levels.

Specific Measures:

Height and weight: Height will be measured using a standard wall mounted, sliding height measuring board (stadiometer). Weight will be measured by an electronic scale.

Body composition: Subject stands in bare feet on an electrode imbedded scale (Tanita) and holds on to electrode imbedded handles. An unnoticeable electrical current is passed through the subject for 2 seconds, from which resistance to electrical flow is measured and body composition is estimated.

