Upon arrival at the laboratory for Sessions 2 and 3, subjects will be asked to ingest a pill containing 10mg of Cetirizine or a gelatin placebo. Black colored (e.g. non-opaque) size 1 gelatin capsules will be purchased commercially. For placebo, the capsules will be filled with 10 mg of sugar-free gelatin, purchased from a local grocery store. Cetirizine will be purchased over-the-counter, and the 10mg pill will be encapsulated within the same black colored size 1 gelatin capsule as the placebo. The treatment will be double-blinded and the order will be randomized and counter-balanced. Pharmacokinetics of Cetirizine indicate peak plasma levels are achieved within 60 min, and as subjects will be at least 3 hours post-prandial, will not be delayed by recent diet.

Maximal oxygen uptake: The subject will be asked to warm up on the cycle ergometer for 10 minutes at a comfortable, self-selected pace. Subjects will be fitted with a) an oronasal face mask which covers the nose and mouth, b) a chest strap heart rate monitor, and c) a pulse oximeter sensor will also be placed on the subject's forehead to non-invasively measure arterial oxygen content. The subject will then be asked to pedal at a cadence between 80 and 110 rpm at a workload of 50W. The workload will be increased by 25W every minute until volitional exhaustion or until RPMs fall below 70 for 3 seconds. Expired air from the face mask is collected in a tube for the determination of oxygen content, CO₂ content, and expired ventilatory volumes.

Constant-load cycling: In sessions #2 and #3, subjects will be asked to complete five minutes of cycling at submaximal workloads equal to 60% and 75% of VO₂max, as determined in session #1. Subjects will have five minutes of passive rest after each 5-minute exercise bout.

5km cycle performance trial: Subject will be asked to complete 5km on the cycle ergometer in as short a time as possible (fit individuals typically take between 8 and 12 minutes). Subjects will be free to shift gears on the cycle and pedal at any cadence desired. Subjects will be given visual feedback on distance travelled and verbal feedback every 1km.

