8.0 Statistical Considerations

Paired t-tests will be used to determine differences between Cetirizine and Placebo trials for select dependent variables (e.g. mass, percent fat). A 2 x 2 (condition by time) repeated measures ANOVA will be used to determine pre- vs. post-test differences across conditions with select dependent variables (e.g. plasma histamine). A 2 x 5 (condition by time) repeated measures ANOVA with a priori simple main effects and a Bonferroni correction for multiple pairwise comparisons will be used to determine differences between conditions for select dependent variables (e.g. ventilation, VO_2 , SpO_2) obtained at each km of the 5km time trials.

A power analysis was completed using previous literature (Prefaut et al., *Med Sci Sports Exerc*, 1997). Their data examined the change in arterial PO_2 levels pre- and post-antihistamine, which relates to our outcome variable of arterial oxyhemoglobin saturation. From their data, we were able to calculate an interventional treatment effect (Cohen's d) of 0.61. Using a one tailed test to match our directional hypothesis, a power analysis with that treatment effect indicates that approximately 9 subjects will provide adequate statistical power (i.e. $1 - \beta > 0.80$) to show significant differences at the $p < 0.05$ level (experiment-wise error rate). With the potential for drop-outs and non-qualifiers after the initial $VO_{2\max}$ screening, we anticipate testing a total of 15 subjects.

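### The crossover contrasts omit session order, so a mean Session 2 to 3 shift above roughly 0.15 to 0.2 SD would cost power; adding a period term is a cheap improvement

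*Combined protocol and SAP*

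**What the plan says.** Section 5.0 gives the capsule at the second and third visits and states that "Sessions 2 and 3 will be randomized and counterbalanced". That is a two-period, two-sequence crossover. Visits are 48 hours to 14 days apart, "all testing sessions will be performed at the same time of day", and caffeine, alcohol, food and hard exercise are restricted beforehand. Session 1 includes one familiarisation 5 km ride in hypoxia. The time trial is self-paced: "Subjects will be free to shift gears on the cycle and pedal at any cadence desired". The dependent variables include "dyspnea and rating of perceived exertion during the 5km TT, time to completion of the 5km TT, power output during the 5km TT".

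Section 8.0 names three analyses:

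- "Paired t-tests will be used to determine differences between Cetirizine and Placebo trials for select dependent variables (e.g. mass, percent fat" being the examples given.
- A 2 x 2 condition-by-time ANOVA for measures such as plasma histamine, taken before and after exercise.
- "A 2 x 5 (condition by time) repeated measures ANOVA with a priori simple main effects and a Bonferroni correction for multiple pairwise comparisons", which "will be used to determine differences between conditions for select dependent variables" recorded at each kilometre.

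In both ANOVAs, time is a position within a session (pre/post, or kilometre), not the order of sessions. No period, sequence or order term appears, and no check for an order effect. Section 8.0 names no test for time-trial completion time. The paired t-test is the only single-value test it describes, so its use for that outcome is an inference.

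**The concern.** Counterbalancing protects the treatment estimate when the two sequences are equal in size, but it does not take a session shift out of the error term. If subjects on average do better or worse in Session 3 than in Session 2, the cetirizine-minus-placebo difference is pushed up in one sequence and down in the other. An analysis without period counts that spread as noise.

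The contrasts exposed are the condition main effect in the 2 x 5 model, the condition contrasts at each kilometre, and any paired comparison of a single-value outcome such as time-trial time. A shift is possible because completion time, power output, ventilation, VO2, dyspnea and perceived exertion all depend on effort in a self-paced ride. It is not expected for body mass or percent fat.

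What is at stake is mainly power in a trial planned around 9 subjects. If the completing sequences are unequal, the error rate for the realised split is at stake too.

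**Working it through.** **Inputs from the documents (Section 8.0).** Effect size 0.61, one-tailed test, 0.05 level, about 9 subjects needed, 15 to be tested.

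**The plan's own figure.** The plan says "we were able to calculate an interventional treatment effect" of 0.61, taken from arterial PO2 data, and does not state the standardiser. Read as a paired effect (mean difference over SD of the difference), a one-sided paired t-test at n = 9 has power 0.51, and 80% would need 19 subjects. Power of 80% at n = 9 needs a paired effect of 0.909. The mismatch is a separate matter. It is the reason for using two effects here, 0.61 and 0.92. Both are assumptions for time-trial outcomes, for which no effect size is given.

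**Assumed, not in the documents.** P is the mean Session 3 minus Session 2 shift in SDs of the within-subject difference, range 0 to 0.5. Splits of 5/5 to 7/7 stand for 10 to 14 completers.

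**Model.** D = tau + P·s + e, with SD(e) = 1, s = +1 if cetirizine comes in Session 3 and -1 if in Session 2.

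- Unadjusted: one-sample t on D, n - 1 df.
- Adjusted for period: average of the two sequence means, pooled within-sequence SD, n - 2 df.

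**Why power falls.** With equal sequences the unadjusted SD grows by about sqrt(1 + P²·n/(n-1)). At n = 14 this is sqrt(1 + P²·14/13) = 1.005, 1.033 and 1.127 for P = 0.1, 0.25 and 0.5.

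**Single-value outcomes, one-sided 0.05, power in %** (adjusted and P = 0 exact from the noncentral t, the rest simulated):

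| Effect | Split | P=0 | P=0.1 | P=0.25 | P=0.5 | Adjusted, any P |
|---|---|---|---|---|---|---|
| 0.61 | 5/5 | 55.4 | 55.1 | 53.2 | 46.9 | 54.7 |
| 0.61 | 6/6 | 63.2 | 62.9 | 61.0 | 54.9 | 62.6 |
| 0.61 | 7/7 | 69.7 | 69.4 | 67.8 | 61.8 | 69.4 |
| 0.92 | 5/5 | 85.0 | 84.7 | 83.5 | 79.0 | 84.3 |
| 0.92 | 6/6 | 91.0 | 90.8 | 90.0 | 86.7 | 90.6 |
| 0.92 | 7/7 | 94.6 | 94.5 | 94.0 | 91.7 | 94.5 |

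There is no loss at P = 0.1. The two analyses break even at about P = 0.15, a little lower or higher by split and effect. The loss is 0.5 to 1.6 points at P = 0.25 and about 3 to 8 points at P = 0.5.

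**2 x 5 condition main effect.** This test equals a paired t-test on each subject's five-kilometre mean. P and the effect must therefore be scaled to the SD of that mean difference. At 7/7, two-sided 0.05:

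- Effect 0.61: 53.5% (P = 0.25) and 46.1% (P = 0.5), against 55.5% adjusted. The loss is about 2 and 9 points.
- Effect 0.92: 87.4% and 83.0%, against 88.4% adjusted. The loss is about 1 and 5 points.

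**Per-kilometre contrasts**, two-sided at 0.05/5 = 0.01 (five comparisons assumed), 7/7:

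- Effect 0.61: 25.5% and 19.1%, against 27.5% adjusted.
- Effect 0.92: 63.3% and 53.9%, against 65.1% adjusted.

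**Condition-by-time tests.** A shift that is constant within a session cancels. Simulated size stayed at 4.9 to 5.1% in the 2 x 5 and 2 x 2 layouts.

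**Unequal sequences.** The unadjusted estimate is displaced by P(n1 - n2)/n, where n1 is the number taking cetirizine in Session 3. At P = 0.5 this is 0.5 × 1/9 = 0.06 at 5/4, 0.5 × 2/10 = 0.10 at 6/4, and 0.5 × 3/9 = 0.17 at 6/3. One-sided size, by direction of the shift, is 4.7% or 2.4% (5/4), 6.2% or 1.7% (6/4), and about 8.7% or 1.2% (6/3). With equal splits it is 3.3%. The adjusted test holds 5% throughout.

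**The case against.** The strongest reply is that the harm rests on a number the documents do not contain. No section gives or suggests a Session 2 to 3 shift. The design works to keep it small, with a hypoxic familiarisation ride, a fixed time of day, pre-visit restrictions, double-blinding and counterbalanced order. With equal sequences, a paired analysis without period is valid and conservative. This stands. It is why the low end of the range is the more likely one, and why the omission is not an error.

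The fix is also not better everywhere. At P = 0.25 and effect 0.61, power averaged over both directions of imbalance is 49.0% unadjusted against 49.8% adjusted at 5/4, 53.3% against 53.3% at 6/4, and 49.1% against 46.5% at 6/3. This stands too. What adjustment secures at such splits is the error rate, not always power.

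The target is partly inferred as well. Time-trial time has no assigned test, the named paired t-test examples should not shift, and the 0.61 comes from oxygenation rather than performance. The 2 x 5 contrasts for ventilation and VO2 are, however, named explicitly.

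Three stronger readings are tempting, and the documents support none of them:

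- A reader might infer that leaving out period biases the comparison or produces false positives. With equal sequences it does neither. With unequal ones the displacement goes either way and averages to zero if the imbalance is random.
- A reader might infer a large loss of power. That needs a shift beyond the range assumed here, and nothing in the documents points to one.
- A reader might extend the point to the histamine condition-by-time interaction. A constant within-session shift drops out of it.

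**Conclusion.** The point holds as a low-cost improvement, with medium confidence. Section 8.0 has no period term for a two-period crossover, and its condition contrasts would lose power if the mean Session 2 to 3 shift exceeded roughly 0.15 to 0.2 SD of the within-subject difference. Below that there is nothing to gain. At the top of the assumed range the cost is modest for single-value outcomes and the 2 x 5 main effect, and somewhat larger for the per-kilometre contrasts (about 8 to 11 points at 7/7).

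Exact balance among completers is not assured: 9 and 15 are both odd, and the plan expects drop-outs. That adds a second reason, since the unadjusted one-sided error rate then depends on the size and direction of a shift nobody has measured.

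The conclusion rests on the assumed shift, on the assumed paired effects of 0.61 and 0.92, and on the inference that time-trial time would be compared by a paired t-test. A period term removes only the mean shift, not individual day-to-day variation.

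**What to change.** In Section 8.0, name the analysis for time-trial time and other effort-dependent single-value outcomes as a model with treatment and period as fixed effects and subject as random. Comparing within-subject differences between the two sequences is equivalent. Include period when testing the condition main effect and the per-kilometre condition contrasts in the 2 x 5 analysis. Leave the condition-by-time tests as they are. Report the number of subjects completing each sequence.

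This needs no new data, visits or subjects, and uses one degree of freedom. If there is no shift, single-value power falls by 0.2 to 0.7 points at 7/7 to 5/5, about 1.3 to 2 points at 5/4 or 6/4, and about 5 points at 6/3. Per-kilometre contrasts at 7/7 lose about 1 point. The cost at 6/3 is a reason to keep the sequences balanced among completers as far as possible.

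### The Bonferroni correction for the per-kilometre condition contrasts has no stated family; naming the five contrasts per variable and using Holm is a cheap improvement

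*Combined protocol and SAP*

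**What the plan says.** Section 8.0 (Statistical Considerations) assigns variables such as ventilation, VO2 and SpO2 to a 2 x 5 repeated measures ANOVA in which "a priori simple main effects and a Bonferroni correction for multiple pairwise comparisons will be used to determine differences between conditions", on values "obtained at each km of the 5km time trials". The contrasts of interest are therefore cetirizine against placebo at a given km, not one km against another.

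The number of comparisons in the Bonferroni family is not given. Nor does the section say whether the correction runs within a km, across the five km, or across variables. The power paragraph of the same section refers to "significant differences at the $p < 0.05$ level (experiment-wise error rate"), which suggests a wider family but does not define one. That paragraph also sets the only stated sidedness: "Using a one tailed test to match our directional hypothesis". The sidedness of the ANOVA contrasts is not stated, and no other section deals with multiplicity.

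**The concern.** A Bonferroni correction is defined only once the number of comparisons is fixed. Here the count could be taken as one (the single cetirizine-placebo pair at a km) or five (the km contrasts within a variable), so the per-km threshold could be 0.05 or 0.01. Left open, that choice could be made after the data are seen.

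The point matters because SpO2 is one of the variables named for this analysis, and arterial oxyhemoglobin saturation is the outcome on which the power calculation rests. The trial is also very small: about 9 subjects are said to be enough and 15 are to be tested. If the family is the five km, a step-down test gives more per-km power at the same error bound without adding a subject.

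**Working it through.** **Inputs from section 8.0.** Two conditions; five km; alpha 0.05; an "interventional treatment effect (Cohen's d) of 0.61"; about 9 subjects for power above 0.80; 15 subjects in total.

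**Assumptions not in the documents.** d is the mean difference divided by the SD of the paired differences, and is the same at each affected km. The correlation r between the paired differences at different km is equal for all pairs of km. Both sidedness options are shown.

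**The plan's own figure.** Paired t-test power is the upper tail of a noncentral t with n - 1 degrees of freedom and noncentrality d√n.
- n = 9, one-tailed 0.05: noncentrality 0.61 × 3 = 1.83, power 0.51. Power of 0.80 needs n = 19.
- The stated 9 is therefore not reproduced on this basis. It can be reached with unstated assumptions, such as d on the raw-score SD with a within-subject correlation of about 0.78. That is a separate matter, and the present point does not depend on it.

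**Threshold under each family.**
- Within a km: one pair, 0.05/1 = 0.05, no correction.
- Across the five km: 0.05/5 = 0.01 per contrast.
- Holm across the five km: compare the ordered p-values with 0.05/5, 0.05/4, 0.05/3, 0.05/2 and 0.05/1 (0.010, 0.0125, 0.0167, 0.025, 0.050), and stop at the first failure. The first step is Bonferroni's threshold and every later one is larger, so Holm rejects whatever Bonferroni rejects.

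**Familywise error per variable if each km is tested at 0.05 and no km has an effect.** If the km are independent: 1 - 0.95^5 = 0.226. With correlation (100,000 simulated trials per scenario, two-sided, n = 9 and 15):

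| r | at least one false km |
|---|---|
| 0.3 | 0.21 |
| 0.5 | 0.19 |
| 0.7 | 0.15-0.16 |
| 0.9 | 0.11 |

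One-sided values are slightly lower: 0.20, 0.17, 0.14 and 0.10.

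**Mean power per km, family of five, d = 0.61 at every km, r = 0.7.**

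| n | sides | Bonferroni | Holm |
|---|---|---|---|
| 9 | two | 0.135 | 0.176 |
| 15 | two | 0.312 | 0.394 |
| 9 | one | 0.213 | 0.282 |
| 15 | one | 0.423 | 0.530 |

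The Bonferroni column can be checked exactly from the noncentral t at alpha 0.01: 0.136 and 0.313 two-sided, 0.214 and 0.424 one-sided.

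**Fewer km affected (r = 0.7, two-sided, power at the affected km, Bonferroni to Holm).**
- Three km: 0.137 to 0.152 (n = 9); 0.311 to 0.342 (n = 15).
- Two km: 0.135 to 0.143; 0.311 to 0.325.
- One km: 0.134 to 0.135; 0.314 to 0.314.

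One-sided, the gain with two or three km affected is about 1 to 4 points.

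**Chance of a finding at one or more km** (all five affected, r = 0.7, two-sided): 0.335 for both methods at n = 9 and 0.588 for both at n = 15. The two methods share the first step.

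**Error control.** With no effect at any km, the two methods have the same familywise error (0.037-0.039 at r = 0.7, two-sided). With three true effects and two nulls it is 0.017-0.018 for Bonferroni and 0.026-0.041 for Holm (r = 0.7, both sidedness options). Both stay below 0.05.

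**The case against.** The strongest defence is that the sentence has a sensible reading and is valid under it. A correction for several comparisons between two conditions only makes sense if the several comparisons are the km contrasts. The experiment-wise phrase, though it sits in the power paragraph, points the same way. Bonferroni over five contrasts then holds the error rate, and it has simple matching simultaneous intervals, which Holm lacks. The gain from Holm is largest when all five km carry the same effect and almost vanishes when only one does.

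All of that stands. A reader might infer that the five tests will go uncorrected and that the trial therefore carries a 10-21% false-positive rate per variable. The documents do not support that: the no-correction reading is possible but less natural, and what can be shown is only that the family is unstated. A reader might also infer that Bonferroni is an error here. It is not; Holm is a more efficient choice.

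The defence does not remove two facts: the count of comparisons is missing, and for testing Holm is never worse than Bonferroni under the same bound.

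**Conclusion.** This is a cheap improvement, not a flaw that invalidates the analysis. Section 8.0 leaves the Bonferroni family undefined. On its natural reading (five contrasts per variable at 0.01) the plan is valid but gives up about 4 points of mean per-km power at n = 9 and 8 at n = 15 two-sided, or 7 and 11 one-sided, if d = 0.61 holds at every km and r = 0.7. Because d is taken on the SD of differences and r is assumed, these sizes are illustrative. That Holm rejects at least as much as Bonferroni does not depend on them.

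Holm will not rescue the trial's power. At n = 9 and 15, one-sided power without any adjustment is only 0.51 and 0.73 per km on these assumptions. A reader might also take a family defined per variable to deliver the experiment-wise 0.05 that section 8.0 mentions. It does not, because several variables go through the same analysis.

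**What to change.** Replace the Bonferroni phrase in section 8.0 with wording such as:

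> For each variable the five condition contrasts (km 1 to km 5) form one family; their p-values are adjusted by Holm's step-down procedure at familywise 0.05, [one-sided / two-sided]. Comparisons between km are not part of the family. Error is controlled within each variable, not across variables.

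Report ordinary 95% confidence intervals beside the Holm-adjusted p-values.

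The cost is a few sentences and no extra subjects or measurements. The one real downside is that Holm has no simple matching simultaneous intervals. If the investigators value those more, keeping Bonferroni is defensible, provided the family of five and the sidedness are written down.

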2.0 Rationale and Specific Aims

Specific Aim #1 – Determine the effect of Cetirizine (Zyrtec®) on exercise performance and arterial oxygenation with acute exposure to a simulated altitude

For this project, healthy subjects will perform steady state and progressive work rate exercise, endurance performance time trials, and repeated sprint performance time trials in the laboratory at a simulated altitude of 3000m (9900ft) after dosing with 10 mg of Cetirizine or a placebo in a repeated measures design. Non-invasive techniques (pulse oximetry, near-infrared spectroscopy [NIRS]) will be utilized to measure changes in arterial oxyhemoglobin saturation and skeletal muscle oxygenation at the level of the microvasculature during exercise.

It is expected that after Cetirizine, blood and muscle microvascular oxygenation during heavy exercise will improve compared to placebo, ultimately improving exercise performance at altitude.

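### The stated power of over 80% with about 9 subjects does not follow from the stated inputs and is tied to no named contrast in the planned SpO2 analysis

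*Combined protocol and SAP*

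**What the plan says.** All of the statistical plan is in section 8.0. The power paragraph takes its effect size from a published antihistamine study of arterial PO2, "which relates to our outcome variable of arterial oxyhemoglobin saturation". From that source, "we were able to calculate an interventional treatment effect (Cohen's d) of 0.61". The calculation is one-tailed at p < 0.05 ("Using a one tailed test to match our directional hypothesis"), and the conclusion is that "approximately 9 subjects will provide adequate statistical power". To cover drop-outs and people who fail screening, "we anticipate testing a total of 15 subjects". The 0.05 is described as an experiment-wise error rate.

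The paragraph before it sets out the analyses. For measurements taken at each kilometre of the time trial, with SpO2 given as an example, the method is "A 2 x 5 (condition by time) repeated measures ANOVA with a priori simple main effects and a Bonferroni correction for multiple pairwise comparisons".

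Section 2.0 states the aim as the effect of cetirizine "on exercise performance and arterial oxygenation with acute exposure to a simulated altitude", in a within-subject design, and expects improvement over placebo.

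The documents do not give the standardiser for d, a within-subject or between-kilometre correlation, an SD of differences, the Bonferroni divisor, the sidedness of the ANOVA tests, or the effect that settles the SpO2 question.

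**The concern.** Two links are missing. The first runs from the inputs to the sample size: in a within-subject design, d gives a number of subjects only once it is known whether it was scaled by the SD of the paired differences or by the raw SD, and in the latter case what correlation applies. The second runs from the power calculation to the analysis: the calculation describes one directional test, while the 2 x 5 ANOVA yields a condition effect, an interaction and up to five per-kilometre comparisons, each with its own power.

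The target of 9 and the plan to test 15 both rest on this figure. A reader cannot tell which SpO2 result it refers to, and an unnamed contrast can be chosen after the data are seen. A secondary point is that Bonferroni is described only for pairwise comparisons within the 2 x 5 analyses, so the reach of the experiment-wise claim across several outcomes is unclear.

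**Working it through.** **Inputs (section 8.0).** d = 0.61; one-tailed 0.05; power above 0.80; about 9 subjects; 15 to be tested. The 15 is counted before drop-outs and non-qualifiers, so it is an upper limit on completers.

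**Step 1: the plan's own figure, as a single paired test.** Power = P(T > t₀.₉₅,ₙ₋₁), where T is noncentral t with n − 1 df and noncentrality d_z√n. Take d_z = 0.61.

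- n = 9: noncentrality 0.61 × 3 = 1.83, critical value 1.860, power **51%**.
- n = 15: noncentrality 0.61 × 3.873 = 2.363, critical value 1.761, power **73%**.
- n = 18 gives 79.9% and n = 19 gives 82%, so **19** are needed. The normal approximation, ((1.645 + 0.842)/0.61)² = 16.6, gives 17.

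Reading 0.61 as a two-group effect moves further away: 34 per group for 80% power, and 34% power with 9 per group. So 9 is not reproduced from the stated inputs alone.

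**Step 2: what recovers 9.** A one-sided paired test with n = 9 has 80% power at d_z = 0.909. I found three routes; each needs an input that the plan does not give.

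- *Raw-SD d, single paired test.* d_z = d/√(2(1 − r)), so r = 1 − (0.61/0.909)²/2 = 0.775. A within-subject correlation of about 0.775 or more is needed. At r = 0.5, 0.7, 0.75 and 0.8 the required n is 19, 12, 10 and 9.
- *One-sided condition effect over 5 km, d_z = 0.61 at each km.* The effect on the 5-km mean is 0.61 × √(5/(1 + 4ρ)), where ρ is the correlation between kilometres of the cetirizine-minus-placebo differences. Setting this to 0.909 gives ρ = (5 × (0.61/0.909)² − 1)/4 = 0.31, so ρ must be at most about 0.31.
- *A generic repeated-measures ANOVA formula.* With f = d/2 = 0.305, 5 levels and ρ = 0.7, λ = 9 × 5 × 0.305²/0.3 = 13.95 on 4 and 32 df, which gives 80% power at n = 9.

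The documents do not show which route, if any, was used.

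**Step 3: how far the answer depends on the contrast.** Take the condition effect (5-km mean difference) with d_z = 0.61 at each km. The correlations are my assumptions.

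| ρ between km | Effect on 5-km mean | One-sided power, n = 9 / 15 | Two-sided power, n = 9 / 15 |
|---|---|---|---|
| 0.3 | 0.920 | 81% / 96% | 68% / 91% |
| 0.5 | 0.788 | 70% / 89% | 55% / 81% |
| 0.7 | 0.700 | 61% / 82% | 46% / 71% |

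Sidedness alone moves power at n = 9 by about 13 to 15 points. Power for a per-kilometre comparison also needs the missing divisor. Power for the interaction needs the pattern of the effect over distance, on which 0.61 gives no information.

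**The case against.** The strongest reply is that the figure may be sound. Step 2 shows that 9 can be reached by more than one reasonable route, and the cited source, which is not available here, may make the standardiser clear. If the plan's 80% at n = 9 is granted (d_z = 0.909 at each km), the two-sided condition effect has 95%, 87% and 78% power at n = 9 for ρ = 0.3, 0.5 and 0.7, and over 96% at n = 15. This stands, and it rules out three stronger readings.

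- A reader might infer that the study is underpowered. The documents do not support that, because the result depends on correlations that they do not give.
- A reader might infer that 9 requires a within-subject correlation of at least 0.775. That holds only for a single paired test with d on the raw-SD scale.
- A reader might infer that the one-tailed calculation contradicts the ANOVA, or that Bonferroni removes the power. The condition effect and each per-kilometre effect have 1 df and could be tested directionally, and section 2.0 states a direction. The plan gives no divisor and does not say that one given kilometre decides.

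It is also fair that the 2 x 5 model is assigned only to per-kilometre values. Section 5.0 has the oximeter fitted before the constant-load bouts as well, so even the SpO2 measurement that was powered is not certain. That supports a missing link between power and analysis rather than a proven mismatch.

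What the reply does not supply is the missing input or the named contrast.

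**Conclusion.** The point holds in this form: the stated power does not follow from the stated inputs and is not tied to the planned SpO2 analysis. As a single one-tailed paired test with d_z = 0.61, power is 51% at 9 and 73% at 15, against a claim of more than 80% at about 9, and 19 subjects are needed. These figures assume only that 0.61 is the paired effect. Everything beyond them rests on an assumed correlation, contrast or sidedness, so no single corrected sample size can be given. Whether the true power is above or below 80% cannot be settled from the documents.

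The experiment-wise wording is secondary. It is ambiguous, and could be meant for SpO2 alone, but the plan does not say so.

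**What to change.** In section 8.0:

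1. Name one deciding SpO2 contrast, for example the cetirizine-minus-placebo difference in mean SpO2 over the 5 km (the ANOVA condition effect), and state whether it is tested one- or two-sided.
2. Define d: either d_z, or the raw-SD d with the assumed within-subject and between-kilometre correlations.
3. Restate power for that contrast at the expected number of completers, over a range of correlations as in the table above.
4. Give the divisor for the per-kilometre comparisons.
5. Limit the experiment-wise 0.05 to the named contrast or to a stated family of tests. If time-trial performance, which the aim names first, is to carry a confirmatory claim, include it in that family.

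The cost is protocol wording and one calculation; study procedures do not change. The downside is that the restated power may be less favourable and could call for more than 9 completers, and that outcomes outside the family carry no confirmatory claim.
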